# **Study population:**

The study will include children attending kindergartens who are aged 5–6 years old and their mothers.

There are 13,583 children enrolled in Al-Ahsa kindergarten schools, the exclusion of special needs schools results in the elimination of 53 children from the study population. Therefore, only 13,530 children will be included.

**Figure 1.** The distribution of kindergartens and children in the Al-Ahsa region based on the relevant educational offices.

### **Study sample:**

Mother-child pair.

#### **Inclusion criteria:**

-Children aged 5-6 years who are registered in the respective academic year at kindergarten

schools in Al-Ahsa.

-Mothers of preschool children who agree to participate and provide consent.

-Children and mothers who can attend all educational sessions.

#### **Exclusion criteria:**

-Special needs kindergartens.

-Illiterate mothers.

-Children with dental anomalies.

-Children with orthodontics appliance.

-Children with systemic diseases (Diabetes mellitus, Hemophilia,

Cancer, Craniofacial anomalies and syndromes).

To avoid deprivation of learning, all children will get oral health education, but they will not be counted in the study sample. Exclusion will occur during the data analysis process.

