#### The oral health education program will be delivered by:

Specialized kindergarten teachers.

Teachers will undergo through a special, well-structured program for preparation, training and calibration.

For children, they will receive the program during regular school hours on weekdays.

**For mothers**, depending on what they prefer, the lecture will either be arranged in person or virtually via the Zoom online platform.

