### In conventional group:

1- A power point presentation will be provided to the children. (One visit)

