### In non-conventional group:

1- Children will be subjected to an interactive learning approach that includes: (Four visits)

-Brain-based learning strategies using storytelling and hands-on activities.

-An online game-based learning platform (Kahoot).

(It can be accessed via a web browser or the Kahoot app).

2-Mothers will be subjected to an oral health education lecture.

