### **Non-conventional Oral Health Education**

1.First Visit: Introduction to the importance of oral hygiene through visual storytelling, depicting a child who experiences dental pain due to poor oral hygiene. And game-based session using puzzle and Kahoot app for question-and-answer activities related to oral hygiene.

2.Second Visit: Explanation of the process of plaque accumulation and hands-on activity where children practice brushing plaque off a paper character to simulate good oral hygiene practices. And game-based session using Kahoot for question-and-answer activities related to plaque accumulation

3. Third Visit: Explanation of the importance and components of the mouth and the right way for brushing teeth including activity on a jaw model to apply the correct brushing technique. And game-based session using Kahoot for question-and-answer activities related to importance and components of the mouth.

4.Fourth Visit: Oral hygiene instruction, how to keep our teeth healthy and reinforcement of preventive measures such as dental visits. And game-based session using memory matching game and Kahoot app for question-and-answer activities related to healthy mouth.

Then, over a period of 3 months, this game will be played online from home in a competitive and group setting once a week.

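### Exclusions are applied at data analysis, after allocation; if the all-sessions criterion is enforced there too, the hurdle differs by arm (one child visit against four)

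*Protocol*

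**What the plan says.** The protocol's Exclusion criteria section lists special-needs kindergartens, illiterate mothers, dental anomalies, orthodontic appliances and certain systemic diseases. It then explains that "all children will get oral health education, but they will not be counted in the study sample", and ends: "Exclusion will occur during the data analysis process".

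The Inclusion criteria section adds an attendance item: "Children and mothers who can attend all educational sessions". What counts as all sessions depends on the arm:

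- Conventional group: "A power point presentation will be provided to the children. (One visit".
- Non-conventional group: "Children will be subjected to an interactive learning approach that includes: (Four visits". The same section adds "Mothers will be subjected to an oral health education lecture".
- After the four visits, "over a period of 3 months, this game will be played online from home in a competitive and group setting once a week".

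The general section on who delivers the programme also mentions a lecture for mothers, without limiting it to one arm: "depending on what they prefer, the lecture will either be arranged in person or virtually via the Zoom online platform".

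Whole classes are allocated to the arms by coin toss (section on sampling at the children level). The trial is described as single-blinded, and the section on ascertainment and observer bias blinds the examiners. No section says when eligibility is checked relative to allocation, or who applies the exclusions.

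**The concern.** Randomisation protects the comparison only if membership of the analysed sample does not depend on anything that happens after allocation. A rule that settles membership at the analysis stage removes that protection in two ways.

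First, whoever applies the listed criteria may know the arm and the outcome. Some of those criteria need judgement; dental anomalies, for example, are not defined.

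Second, the attendance item refers to a schedule that a family has only once its class is allocated, and that schedule is longer in the non-conventional arm. If the item is checked at analysis against sessions actually attended, that arm loses more of its less adherent families. Such families plausibly have poorer child hygiene scores and poorer maternal knowledge, attitude and practice scores. Removing more of them from one arm would move the comparison towards the superiority stated in the Hypothesis section, even if the programmes were equally effective.

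**Working it through.** **The plan's own figures.** From the Sample size section: 788 + 78 = 866 pairs, and 866/2 = 433 per arm. The base requirement is 788/2 = 394 per arm, so the 10% allowance is 39 pairs per arm. The protocol describes this allowance as cover for dropout. It gives no attendance rate, effect size or SD, so everything below is illustration.

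**Step 1: pairs kept if full attendance were enforced and misses were independent.** With attendance p per session and k required sessions, the share kept is p^k.

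| Assumed p | Conventional, k = 1 | Non-conventional, k = 4 |
|---|---|---|
| 0.99 | 429 | 416 |
| 0.98 | 424 | 399 |
| 0.95 | 433 × 0.95 = 411 | 433 × 0.8145 = 353 |
| 0.90 | 390 | 284 |

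At p = 0.95, counting the mothers' lecture in the non-conventional arm only (1 against 5 sessions) gives 411 against 335. Counting it in both arms (2 against 5) gives 391 against 335.

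**Step 2: bias under a single consistent model.** Independent misses lose pairs but cause no bias, because a miss then says nothing about the family. Bias needs a trait that links attendance to outcome. Let T be standard normal. A session is attended when √ρ·T + √(1−ρ)·e > −z, where e is an independent standard normal error for each session and z = Φ⁻¹(0.95) = 1.645. Then:

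- attendance given T = t is a(t) = Φ((1.645 + √ρ·t)/√(1−ρ));
- the share kept after k sessions is q_k = E[a(T)^k];
- the mean trait among those kept is m_k = E[T·a(T)^k]/q_k;
- the bias in outcome SDs is r × (m_k non-conventional − m_k conventional), where r is the trait–outcome correlation.

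At 95% attendance, each bias range runs from r = 0.2 to r = 0.3:

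| ρ | Kept of 433, k = 4 | Bias, 1 v 4 | Bias, 1 v 5 | Bias, 2 v 5 |
|---|---|---|---|---|
| 0.1 | 355 | 0.019–0.028 | 0.025–0.037 | 0.018–0.027 |
| 0.3 | 362 | 0.027–0.041 | 0.034–0.051 | 0.024–0.036 |
| 0.5 | 371 | 0.027–0.041 | 0.034–0.050 | 0.022–0.034 |
| 0.7 | 381 | 0.023–0.034 | 0.027–0.041 | 0.017–0.026 |
| 0.9 | 395 | 0.013–0.020 | 0.016–0.023 | 0.009–0.014 |

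With k = 1, 411 pairs are kept whatever ρ is. The bias vanishes at both extremes: at ρ = 0 misses are random, and at ρ = 1 the same families miss every session, so both arms are cut alike. Across the table the bias is about 0.01 to 0.05 SD. The assumed attendance rate matters: for 1 against 4 sessions the same model gives about 0.005 to 0.013 SD at 99% and 0.02 to 0.07 SD at 90%.

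**The case against.** The strongest reply is that the protocol never says non-attenders are removed. The attendance item speaks of ability to attend and stands beside consent, so it can be read as a condition of enrolment. The timing sentence closes a list that does not include attendance, and its purpose is to let every child in a class be taught. The listed criteria are baseline traits, mostly objective, which the number of sessions cannot change, so applying them late need not affect the arms differently. Children's sessions fall in regular school hours, so missing one is largely school absence. The weekly home game is not called an educational session. Analysis as allocated and sensitivity analyses are commonly left to an SAP, which is not shown here.

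Much of this stands. A reader might infer that the non-conventional arm will be cut down to its most compliant families. The documents support that only as a possible reading, and the lecture cannot be counted as a clear difference between arms.

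A reader might also put retention of 81% or 77% through a cut on one compliance trait and obtain a bias of 0.04 to 0.08 SD, or 20–40% of a 0.20 SD effect. That calculation takes retention from independent misses and then treats the misses as wholly trait-driven, which cannot both hold. The 0.20 SD benchmark is not in the protocol either. A two-sided standardised difference of 0.2 happens to give 786 pairs, close to 788, but no effect size is stated.

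The reply does not remove the timing rule. It is stated outright, no eligibility check before allocation is described, and blinding is stated only for examiners. The contrast of one against four child visits is also explicit. The finding rests on these statements and not on anything left to an SAP.

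**Conclusion.** The point holds in a conditional form. It is certain that the protocol places exclusion at the analysis stage, after allocation and with outcomes in hand, and describes no safeguard. It is possible, but not stated, that the all-sessions item is enforced at the same stage. If it is, the arms face unequal hurdles and the bias would favour the stated hypothesis.

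Its size cannot be derived from the protocol. At an assumed 95% attendance per session and a trait–outcome correlation of 0.2 to 0.3, the bias is about 0.01 to 0.05 SD. Under independent misses the loss is 411 against 353 pairs kept of 433, and 353 is below the base 394 per arm before any dropout. With near-complete attendance both effects are small. This should be fixed, with moderate confidence, because the rule is avoidable and cheap to change.

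**What to change.** 1. **Inclusion criteria.** Replace the attendance item with willingness to attend the sessions of whichever programme the class is given, stated at consent and worded identically for both arms.
2. **Exclusion criteria, last sentence.** Replace it with wording such as: *Eligibility is determined from baseline information before the class allocation is revealed. All children are still taught. All eligible consented pairs are analysed in the arm to which their class was allocated, whatever number of sessions they attended.*
3. **Attendance.** Record it as a measure of adherence, and use a full-attendance analysis only as a sensitivity analysis.
4. **Mothers' lecture.** Reconcile the delivery section with the two group sections, so that it is clear which arms' mothers receive it.

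Teaching every child, the reason given for late exclusion, does not depend on when eligibility is decided. The Measurements section already schedules an examination before the intervention and a parental questionnaire before the study, but its questionnaire topics do not include systemic disease or maternal literacy. Those items should be added if they are not already there. Beyond that the cost is wording, and possibly a slightly smaller estimated effect because non-attenders stay in the analysis.

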#### Sample size:

The calculation of the sample size for this study was conducted using the OpenEpi (openepi.com). The expected sample size will be 788 mother-child pair at a power of 0.80 and an alpha error of 0.05. To increase the statistical power and account for dropout during the follow-up period, the sample size will be raised by 10%, resulting in an additional 78 mother-child pair. Thus, the total sample size of this study will be 866 mother-child pair. These participants will be divided equally into two groups conventional group and non-conventional group. Each group will consist of 433.

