#### Sampling technique:

In this study we will use a multi-stage stratified random sampling technique.

-At the educational offices level: All three educational offices will be included.

-At kindergarten level: Cluster sampling using stratified proportional sampling technique. This study will include ten kindergartens. The number of kindergartens was determined based on a comprehensive assessment, taking into consideration each educational office's weight and the extent of its children enrollment. This method will ensure that the sample size from each office is distributed proportionally by accounting for the public and private strata.

To select kindergartens from each education office, we will use the Simple Random Sampling (SRS) technique. The names of kindergartens will be listed, assigning a number to each KG. A computer random numbers generator will be used to randomly select KGs to be invited to take part in the study.

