#### -At the children level:

Using a computerized random number generator.

Classes will be randomly allocated into the two study groups (conventional and nonconventional) using a a coin toss.

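### The 80% power stated for 788 pairs is not supported for a class-randomised trial: no outcome, effect size, intracluster correlation, class size or design effect is given

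*Protocol*

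**What the plan says.** The Sample size section gives one calculation: "The expected sample size will be 788 mother-child pair at a power of 0.80 and an alpha error of 0.05". It names the software but not the outcome, the difference sought, the SD or rates, or whether the test is one- or two-sided. The only inflation follows: "the sample size will be raised by 10%, resulting in an additional 78 mother-child pair", for a total of 866. The section gives this 10% two purposes, raising power and covering dropout; the later text on loss to follow-up mentions dropout only. On the arms it says: "These participants will be divided equally into two groups conventional group and non-conventional group", 433 in each.

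The unit of randomisation appears under the heading on the children level: "Classes will be randomly allocated into the two study groups (conventional and nonconventional) using a a coin toss". The education sessions are also delivered to groups of children at school, by kindergarten teachers.

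The Data analysis section names t-tests for continuous outcomes and Chi-squared tests for categorical ones, with no term for class or kindergarten.

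The number of kindergartens is not settled. The Sampling technique section says "This study will include ten kindergartens", while the sampling fraction under Private kindergartens uses 14.

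**The concern.** Children in the same class share a teacher, the teaching sessions and the group games, so their outcomes are likely to be correlated. When whole classes are allocated, that correlation reduces the information in a given number of pairs. A power statement for such a design needs an ICC and a class size, and this protocol gives neither.

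Two things are at stake. If the analysis is adjusted for class, a non-significant result would be read against a promise of 80% power that the design may not meet. If it is not adjusted, as the Data analysis section now reads, the nominal 5% error rate does not hold.

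**Working it through.** **Inputs from the protocol.** 788 pairs (394 per arm), power 0.80, alpha 0.05, 10% uplift to 866, equal arms, classes as the unit of allocation.

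**Assumptions, none given in the protocol.** Two-sided test; difference of 0.20 SD (see step 1); m = 20 children analysed per class; ICC 0.01 to 0.10.

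**Step 1: can 788 be reproduced?** Not from the document, because the effect size is missing. Trying an individually randomised two-sample t-test with d = 0.20, two-sided 0.05 and 80% power gives 393.4 per arm, rounded up to 394, so 2 × 394 = 788 (power at 394 per arm: 80.06%). The normal formula gives 393 per arm, 786 in total. The figure can thus be reached with no allowance for clustering, but the match does not prove where it came from.

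**Step 2: power with classes allocated.** Design effect DE = 1 + (m − 1) × ICC. Non-centrality = d × √(N / (4 × DE)). Power comes from the non-central t with (N/m − 2) degrees of freedom. For example, with N = 779 and ICC 0.05: DE = 1 + 19 × 0.05 = 1.95; effective N = 779/1.95 = 399; non-centrality = 0.20 × √(399.5/4) = 2.00; 39 classes, 37 degrees of freedom; power 49.5%.

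| ICC | DE | Power at 788 | Power at 866 (no loss) | Power at 779 (10% loss) | Difference detectable with 80% power at 779 |
|---|---|---|---|---|---|
| 0.01 | 1.19 | 70.8% | 75.0% | 70.3% | 0.225 SD |
| 0.02 | 1.38 | 64.4% | 68.7% | 63.8% | 0.242 SD |
| 0.05 | 1.95 | 49.9% | 53.9% | 49.5% | 0.288 SD |
| 0.10 | 2.90 | 36.2% | 39.3% | 35.8% | 0.351 SD |

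With class sizes of 15 to 25 at 779 pairs, power runs from about 73% (15 per class, ICC 0.01) to 31% (25 per class, ICC 0.10).

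**Step 3: can the 10% uplift cover the clustering?** It covers a design effect of at most 866/788 = 1.099. At 20 per class that is an ICC of 0.099/19 = 0.005, and only if nobody is lost.

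**Step 4: the tests as named.** An ordinary test that ignores class has a false-positive rate of about 2 × [1 − Φ(1.96/√DE)]. At 20 per class this is 7%, 10%, 16% and 25% for ICC 0.01, 0.02, 0.05 and 0.10.

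**Step 5: dropout arithmetic.** 788 × 1.10 = 866.8, stated as 866. After 10% loss, 866 × 0.9 = 779, which is below 788; keeping 788 would take 788/0.9 = 876. On the individual basis of step 1, 779 pairs give 79.6% power rather than 80%, a trivial difference.

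**The case against.** The strongest reply is that the protocol never says 788 is an individually randomised figure. That is right. Other inputs reach the same number: 24% versus 33% by the uncorrected two-proportion formula gives 393.7 per arm, and a design effect of 2 applied to 394 pairs (197 per arm, about 0.28 SD) also gives 788. A reader might infer from the exact match with 0.20 SD that clustering was certainly ignored, but the document cannot settle this. What stands is that no allowance for class allocation is shown, so the power claim is unsupported.

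A reader might also infer that the trial would miss its target effect about half the time. That is a single combination (20 per class, ICC 0.05) in a wide range, and it presumes a class-adjusted test that the Data analysis section does not name. With the ordinary tests named there, on 788 pairs at 0.20 SD and 20 per class, the chance of p < 0.05 would be about 78% to 69% over ICC 0.01 to 0.10. The price is the inflated false-positive rate in step 4. As written, the more direct danger is false positives.

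A separate analysis plan may specify a class-adjusted model, and baseline adjustment or stratification by kindergarten could recover some power. Neither possibility supports the protocol's own power statement, which rests on nothing shown.

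Finally, the dropout shortfall is immaterial, and if losses fall below 10% the uplift does add some power. Both points are accepted.

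**Conclusion.** The point holds in this form: the protocol claims 80% power for a design that allocates classes, without showing any input that such a claim needs. High confidence attaches to the missing allowance. The size of the shortfall is conditional. If 788 is the individually randomised size for 0.20 SD, any positive class ICC puts power for that effect below 80% at 788 pairs under an analysis that allows for class. With 20 per class and ICC 0.01, 0.02, 0.05 and 0.10, power is about 75%, 69%, 54% and 39% if all 866 pairs are retained, and about 70%, 64%, 50% and 36% at 779. The difference detectable with 80% power at 779 is then about 0.22 to 0.35 SD. ICC, class size and effect size are all assumptions of this review. The dropout arithmetic is a minor matter of wording.

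**What to change.** - Restate the Sample size section. Name the outcome and the difference behind 788, the expected number and size of classes, and an assumed ICC with a range.
- Before fixing the number of classes, reconcile the ten kindergartens in Sampling technique with the 14 in the sampling fraction.
- Give the resulting power, or the detectable difference, and label each figure with the N it uses: 866 if all are retained, 779 after 10% loss.
- Tie the statement to an analysis that allows for class, and amend the Data analysis section to match. A power figure for a class-adjusted test should not sit beside ordinary t-tests and Chi-squared tests.
- Minor: state that 866 leaves 779 after 10% loss, and do not also credit the same 10% with raising power if that loss occurs.

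The cost is rewording and one recalculation. The stated power will be less favourable, and the analysis commitment changes from simple tests to class-adjusted ones. No extra pairs are required in order to state the power honestly.

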# **Systematic errors**

# Loss of follow-up

This is the main issue because it is a follow-up study.

Minimize by:

**In design level:** Sample size will be raised by 10% to account for any participant loss during the follow-up period.

In conducting level: Maintaining good communication and offer incentives.

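### The 866 pairs leave the required 788 only if total loss stays at or below 9.0%, and the same 78 extra pairs are also credited with raising power

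*Protocol*

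**What the plan says.** Under Sample size, the protocol sets the target: "The expected sample size will be 788 mother-child pair at a power of 0.80 and an alpha error of 0.05". It then gives the reason for enlarging it: "To increase the statistical power and account for dropout during the follow-up period, the sample size will be raised by 10" per cent, "resulting in an additional 78 mother-child pair". The result is that "the total sample size of this study will be 866 mother-child pair", split equally: "Each group will consist of 433".

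Under Systematic errors, Loss of follow-up, where attrition is called the main issue, the design-level remedy is the same increase: "Sample size will be raised by 10% to account for any participant loss during the follow-up period". Good communication and incentives are listed as conduct-level measures.

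Under Exclusion criteria, ineligible children still receive the education but are placed outside the study sample, and the timing is given as: "Exclusion will occur during the data analysis process". No expected number of exclusions appears.

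Under Study population, 13,583 enrolled children become 13,530 by removing only the 53 in special needs schools. Under Sampling technique, the child-level sampling fraction is 866/13530 = 0.064, described as each child's chance of being selected.

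**The concern.** Three features make the 866 look safer than it is.

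- The target is multiplied by 1.10. Keeping 788 after a 10% loss requires dividing by 0.90, which gives a larger number.
- The same 78 pairs are meant both to replace dropouts and to add power. A pair that replaces a dropout restores the planned power and does not add to it.
- Eligibility is applied at analysis. If 866 is the number drawn, pairs with an illiterate mother, a dental anomaly, an orthodontic appliance or a listed systemic disease also come out of the 866, and nothing is set aside for them.

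A reader would take 866 as protecting 0.80 power against any participant loss. The question is how much loss it actually tolerates.

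**Working it through.** **Inputs.** From Sample size: target 788 pairs (394 per arm), power 0.80, alpha 0.05, 78 extra pairs, total 866 (433 per arm). From Study population and Sampling technique: frame 13,530, sampling fraction 866/13530. Not in the protocol: effect size, sidedness, expected dropout rate, expected exclusion rate. A two-sided test is assumed below.

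**Reproducing the plan's figure.** 10% of 788 = 78.8, cut to 78. 788 + 78 = 866, and 866/2 = 433. The form used is N × (1 + 0.10) = 866.8, rounded down.

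**Loss that 866 can absorb.** 866 × (1 − L) ≥ 788 gives L ≤ 1 − 788/866 = 78/866 = 9.0%. This needs no effect size.

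**If the loss were 10%.** 866 × 0.90 = 779.4, so 779 pairs, 9 fewer than 788. Per arm, 433 × 0.90 = 389.7 against 394. Full cover needs 788/0.90 = 875.6, so 876 pairs (438 per arm), 10 more than planned. Rounding 78.8 up would not close the gap: 867 × 0.90 = 780.3.

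**Effect on power.** The 788 cannot be rebuilt because no effect size is given. Fix the effect instead so that 788 gives 0.80, and use the normal approximation, treating children as independent:

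power(n) = Φ[(1.960 + 0.842) × √(n/788) − 1.960]

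| Evaluable pairs | Power |
|---|---|
| 866 (no loss) | 83.6% |
| 788 (9.0% loss) | 80.0% |
| 779 (10% loss) | 79.5% |

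The cost at a 10% loss is about 0.5 percentage points.

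**Are exclusions inside the 866?** The sampling fraction treats 866 as the number drawn from 13,530. That frame had only special needs schools removed, so it still holds the other ineligible pairs. Sample size then divides the 866 into arms, and exclusion follows at analysis. Read this way, exclusions reduce the 866. Against this, excluded children are said to fall outside the study sample, which could mean that 866 is a count after exclusion.

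**If they are inside.** With dropout d and exclusion e, evaluable pairs = 866 × (1 − d) × (1 − e). The exclusion rates below are assumptions that show a range.

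| Assumed e | Largest d that keeps 788 | Evaluable pairs if d = 10% |
|---|---|---|
| 0% | 9.0% | 779 |
| 1% | 8.1% | about 772 |
| 2% | 7.1% | about 764 |
| 5% | 4.2% | 740 |
| 10% | none (866 × 0.90 = 779.4 before any dropout) | 701 |

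**The case against.** The strongest reply is that the protocol never names an expected loss rate. Ten per cent is the size of the increase in both places where it appears, and 788 + 78 = 866 is correct apart from the rounding. This stands. A reader might infer that 866 fails to leave 788 evaluable pairs, or that the stated power is lost. The documents support neither as a flat statement: at a total loss of 9.0% or less, 788 or more pairs remain.

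It is also fair that the two purposes are not strictly incompatible. With no loss, 866 gives about 83.6% power, so some gain is possible when attrition is low. What the allowance cannot do is raise power and also be fully spent on dropouts.

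On exclusions, a reader might infer that the 78 pairs must absorb them. The sampling fraction and the timing of exclusion favour that reading, but the remark placing excluded children outside the study sample prevents certainty. The special needs criterion takes nothing from the 866, because those schools are already out of the frame. Any exclusion rate is a guess, and power figures built on one would also need an effect size that the protocol does not give.

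Finally, the shortfall from the inflation form alone is small: 866 against 876 is about 1.2%. The protocol also plans conduct-level measures to limit attrition. Both points stand, and they keep this a minor finding.

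**Conclusion.** The point holds in a limited form. The 866 preserves 788 evaluable pairs, and with them 0.80 power on the protocol's individual-level terms, up to a total loss of 9.0% and no further. If the 10% increase was meant to cover a 10% loss, it falls 9 pairs short and costs about 0.5 percentage points of power. That is negligible by itself. The shortfall would become material only if exclusions of more than a few per cent come out of the same 866, and the protocol neither settles that nor gives a rate.

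The 9.0% limit rests only on the protocol's own numbers. The power figures assume a two-sided test, an effect fixed so that 788 gives 0.80, and independent children. The last is the protocol's apparent basis, although classes are what is allocated. The clause promising more power overstates what the allowance is sure to deliver.

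**What to change.** 1. In Sample size and in Loss of follow-up, state that 866 drawn pairs leave 788 evaluable only if dropout and analysis-stage exclusions together do not exceed 9.0%.
2. In Sample size, delete the opening clause that credits the increase with raising power.
3. In Exclusion criteria or Sample size, state whether 866 is counted before or after the exclusions.
4. If expected dropout and exclusion rates are adopted, give the resulting evaluable number, 866 × (1 − dropout) × (1 − exclusion), and restate the power from the sponsor's own effect size. Power figures that rest on a reviewer's assumed effect or exclusion rate should not be printed in the protocol.

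The cost is a few sentences and possibly a slightly lower stated power. No extra enrolment is needed.
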